10.6. Efficacy Analysis

Descriptive statistics will be used to summarize the data. Continuous variables will be presented showing number of observations available, mean, median, minimum, maximum, and standard deviations (or standard errors, depending on the variable) by visit. Categorical variables will be presented showing frequencies and percentages by visit.

All tests will be 2-sided and use $\alpha = 0.049$ for the final analysis to accommodate planned interim analyses for which $\alpha = 0.001$ is allocated, thereby preserving a study-wise over all $\alpha = 0.05$. A statistical penalty is imposed for interim analysis. This penalty is applied regardless of whether or not there is an actual modification to the study structure, design, or analysis plans. It is noted that in this adaptive study, modification is permitted with documentation and justification.

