10.10. Interim Analysis

An Interim Analysis Plan (IAP) will be developed prior to any unblinding of the Part 1 results (other than emergency unblinding for safety reasons). The IAP will describe the statistical methodological approach, disclosure controls, and processes intended to protect the integrity of the ongoing study. The interim analysis will follow the IAP.

An interim analysis is planned for Part 1 of this study approximately 6 weeks after approximately 20 patients have been randomized. Additional interim analysis may or may not be done. Interim analysis may or may not be unblinded. As a conservative measure to protect against alpha inflation, an adjustment of 0.001 is made to the study-wise alpha that may or may not be done.

In this adaptive study, analysis will occur for the parts of the study separately as defined. There is an adjustment for alpha as a conservative measure to control unexpected inflation of alpha, reserving 0.049 for the final analysis.

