1.10 Early Stopping, Data Monitoring, and Interim Analysis

This study has accommodation for one or more interim analyses. If an interim analysis is done, a separate interim analysis plan will include details of the planned analyses, disclosure, and plans to protect the integrity of the ongoing study.

Interim analysis may or may not be done for business purposes in any portion of this protocol.

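### The flat 0.001 interim allowance does not protect the 5% level if Part 2 is changed after an unblinded look at Part 2 data, which is not planned but not excluded

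*Protocol*

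**What the plan says.** Protocol 10.6 sets two-sided 0.049 for the final analysis and 0.001 for interim analyses, and says that this preserves an overall 0.05. It continues: "This penalty is applied regardless of whether or not there is an actual modification to the study structure, design, or analysis plans". The next sentence reads: "It is noted that in this adaptive study, modification is permitted with documentation and justification". SAP 7 repeats the split and the penalty sentence.

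The one look described in advance is in Part 1 (protocol 10.10). The same section adds: "Additional interim analysis may or may not be done. Interim analysis may or may not be unblinded". SAP 1.10 extends the scope: "Interim analysis may or may not be done for business purposes in any portion of this protocol".

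Protocol 3.2.2 names endpoints and patient numbers as the features of Part 2 that may change. Neither document gives a combination test, a conditional-error rule or a closed test. Interim methods are left to a separate interim analysis plan.

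**The concern.** A 0.049/0.001 split pays for one thing: the chance of declaring success at an interim look as well as at the end. It does not pay for using unblinded results to choose the endpoint or sample size when the same patients then count in the final test. The final statistic is then partly selected on its own data, and the ordinary critical value is too lenient.

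The documents claim error control whether or not something is modified, permit modification without listing which kinds, and leave open further looks that may be unblinded and may fall in Part 2. If that route were taken, a Part 2 result at p < 0.049 could not be defended as significant at 5%. The issue is data-dependent change. It is separate from the number of endpoints in the SAP's testing sequence.

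**Working it through.** **The plan's own figure.** 0.049 + 0.001 = 0.050, so the stated total reproduces. It presumes that 0.001 is the total for all looks; if it were spent at each look, two looks would give 0.049 + 2 × 0.001 = 0.051.

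**Inputs from the documents.** Two-sided final level 0.049, critical value c = 1.969. Part 2 planned at 90 (SAP 1.7). Enrolment cap about 140: protocol 3 applies it to the whole study, leaving 140 − 6 − 30 = 104 for Part 2; protocol 5.3 applies it to Parts 1 and 2, leaving 140 − 30 = 110. The HbA1c power calculation needs 68 (protocol 10.2).

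**Assumptions, not in the documents.** An unblinded Part 2 look at 50-75% of the data for the endpoint switch, and at 45 or 60 of 90 patients (50% or 67%) for the size change; two candidate endpoints with correlation 0.3-0.7; a final test on all Part 2 data at 0.049 with no adjustment. All figures are for the final test under the null; spending the interim allowance adds at most 0.1 percentage point.

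**1. Unblinded look at Part 1 only, Part 2 tested alone.** The Part 2 statistic is independent of the data that drove the change. Simulating an endpoint switch gives 4.9%: no inflation.

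**2. Endpoint switch after an unblinded Part 2 look.** Let t be the fraction of data at the look. For each endpoint, Z_final = √t·Z_look + √(1−t)·Z_after. Keep the endpoint with the larger |Z_look| and reject if its |Z_final| > c. With 1,000,000 simulated trials per cell, the two-sided error is:

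| Look at | Correlation 0.3 | 0.5 | 0.7 |
|---|---|---|---|
| 50% | 7.9% | 7.6% | 7.2% |
| 75% | 8.8% | 8.5% | 7.8% |

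**3. Sample-size change after an unblinded Part 2 look.** With n1 patients at the look and final size N, the conditional rejection probability given z1 is

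Φ(−(c√N − √n1·z1)/√(N−n1)) + Φ((−c√N − √n1·z1)/√(N−n1)).

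For each z1, take the N in the allowed range that maximises this, then integrate over the standard normal density of z1:

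| Allowed N | Look at 45 | Look at 60 |
|---|---|---|
| 90 (fixed) | 4.9% | 4.9% |
| 90-104 | 5.2% | 5.3% |
| 90-110 | 5.3% | 5.5% |
| 68-104 | 6.0% | 6.5% |

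These are upper bounds, because they assume the least favourable choice of N at every interim result.

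**4. Inverse-normal test.** Under the 68-104 rule, weights fixed at n1/90 and 1 − n1/90 give 4.9% at either look (simulation).

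**5. If Part 1 were pooled into the confirmatory test.** Part 1 would be 30/120 = 25% of the data. An endpoint switch after unblinding Part 1 would then give 6.1-6.5% at correlation 0.7 down to 0.3, and choosing a total of 120-140 patients would give 5.1%. The harmlessness of Part 1-driven changes therefore depends on keeping Part 1 out.

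**The case against.** The strongest reply is that the documents place adaptation before Part 2 data exist. The synopsis ties Part 2 modifications to Part 1 results, with an amendment and IRB review before Part 2 starts. Protocol 10.4 puts hypothesis changes at the start of Part 2 dosing. Protocol 10.9 keeps the sponsor's Part 1 and Part 2 safety reviews blinded, and 12.1 puts database lock before unblinding. SAP 1.11 says its own changes rested on blinded evaluations, and SAP 1.2 gives the pooled analysis no alpha. All of this stands, and it makes the problem a gap in the rules. None of it forbids a later look or change.

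The penalty sentence can also be read modestly, as saying that the cost is paid even if nothing changes. That reading is fair, but the claim that 0.05 is preserved comes directly before it and the open permission to modify directly after it, so the text needs the limit spelled out.

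The interim analysis plan might supply an adjusted test. It was not available for this review. The two documents assert control without making it conditional on such a test.

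A reader might infer that any unblinded look followed by a change raises the error, or that the error will be 6-9%. Neither is supported. The planned Part 1 look leaves a Part 2-only test at 4.9%. Enlarging Part 2 within the cap costs a few tenths of a percentage point at most. Still larger sample-size figures require an unlimited Part 2, which the cap contradicts.

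**Conclusion.** The concern holds in a limited form. The claim of 0.05 regardless of modification is correct for changes based on Sentinel or Part 1 data (with Part 1 outside the confirmatory test) and for changes based on blinded data. It is not correct for a change to Part 2 after an unblinded look at Part 2 data, a route left open though not planned. The exposure is about 7-9% two-sided for a switch between two endpoints, 5.2-5.5% for a size increase within the cap, and 6.0-6.5% if the size may also fall to 68. No document proposes cutting Part 2 to 68; that figure is only the HbA1c power requirement. The sizes depend on the assumed look timing and endpoint correlation and describe what could happen. Nothing in the documents shows that a change of this kind was made. The wording should be corrected because the plan states an error property that it does not secure for everything it allows.

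**What to change.** In protocol 10.6 and 10.10 and SAP 1.10 and 7, replace the claim that the penalty suffices regardless of modification with three rules:

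1. Part 2 sample size, endpoints, hypotheses and analysis rules may be changed only on Sentinel or Part 1 data or on blinded Part 2 data. No change may follow from an unblinded look at Part 2.
2. The 0.001 covers all unblinded Part 2 looks together.
3. The confirmatory test uses Part 2 data only. Protocol 10.2, repeated in SAP 1.9, speaks of 120 patients in the Part 2 analyses, which equals 30 + 90; reconcile this.

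If the sponsor wants to keep the option of a change after an unblinded Part 2 look, replace the ban in rule 1 with an inverse-normal combination test specified before the look. Fix both the look time and the weights in advance, since the planned 90 alone does not determine the weights. Add closed testing if the endpoint may change.

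The cost is wording. The sponsor gives up penalty-free changes after an unblinded Part 2 look, or accepts some loss of efficiency from fixed weights. Since SAP 1.11 attributes the changes so far to blinded evaluations, nothing already planned is lost.

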10.6.1. Efficacy Variables of Analysis

In Part 1, the primary variable of analysis for the interim analysis is mean change from baseline in bolus insulin (number of units) or the time in target glycemic range.

In Part 2, and also in the integrated Part 1 and Part 2 analysis, the primary variable of analysis is mean change from baseline in HbA1c at 12 weeks.

Other variables of analysis include will be defined in the SAP.

10.6.2. Statistical Methodology for Primary Analysis

The primary analysis will use the intent-to-treat methodology and a main-effects model for analysis of covariance (ANCOVA), with adjustment for baseline HbA1c levels. Interaction terms will be examined in supportive analyses. In the event of a significant interaction term, the impact on analysis conclusion will be examined. The primary model will not include interaction terms. Assumptions underlying ANCOVA will be examined. If assumptions of ANCOVA are unwarranted and the validity of the ANCOVA becomes questionable, rank analogues will be advanced as the primary analysis. Multiple imputation (MI) methods will be used to handle missing data.

For completeness, an observed cases analysis will be done by visit in which no data are excluded, no data are imputed, and no data are represented at times other than when they were observed. As an alternative for handling missing data according to the rules of the primary analysis, a supportive analysis will be done using last-observation-carried-forward (LOCF).

For statistical analyses, 95% confidence intervals will be produced for the least squares means (LSM) in each treatment group, as well as the LSM differences as compared to placebo. For MMRM and ANCOVA, two-sided p-values will be displayed for the comparison against placebo.

Suspicious values that appear invalid and outliers that are detected during the blind review of the data will be investigated. Methods for dealing with invalid data and outliers will be defined in the SAP, prior to unblinding. Data considered to be invalid will be set to missing. In general, except for imputation methods specifically described in this protocol, missing data will not be imputed; outliers will not be excluded unless they are considered to be erroneous or invalid values. Sensitivity analyses and exploratory analyses may be done using imputation or excluding invalid data or outliers to ensure robustness of study conclusions.

10.6.3. Statistical Methodology for Secondary and Other Efficacy Analysis

Efficacy analysis for other variables that are continuous will use ANCOVA with baseline measures as covariates, with a main effects model. Dichotomous measures (e.g., proportions of responders) will be done on the full analysis set (FAS), consisting of all randomized patients who receive at least one dose of randomized study medication. Fisher's exact test will be used at the study level for variables of analysis that are proportions. Patients obtaining achievement of the response criterion prior to Week 12 will be considered responders; all others will be considered non-responders. No imputations methods will be necessary.

For secondary variables, confidence intervals will be calculated for each group and for differences between the placebo group and the group treated with TTP399.

Subgroup Analyses

Subgroup analyses will be done as identified in the SAP.

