2.3. Parts 1 and 2 (Following 12 weeks of dosing)

Objectives

Primary Objective:

- To evaluate the pharmacodynamic (PD) effect of TTP399 following multiple day dosing (at 12 weeks) in patients with T1DM

Secondary Objectives:

- To evaluate the safety and tolerability of TTP399 administered for 12 weeks in T1DM patients

Exploratory Objectives

- Assess relevancy of non-genomic biomarkers in predicitng responders and efficacy
- To assess changes in patient quality of life

Endpoints (Part 1 and Part 2)

Primary Endpoint:

- Change from baseline in HbA1c at 12 weeks

Secondary Endpoints:

- Change from baseline time in target glycemic range (70-180 mg/dL); hyperglycemic range (Level 1 > 180 mg/dL; Level 2 (>250mg/dL) and hypoglycemic range (Level 1 < 70mg/dL; Level 2 < 54 mg/dL)
- Change from baseline in number of units of insulin (basal, bolus or total daily) dose
- Percent change from baseline in insulin (basal, bolus or total daily) dose
- Achievement of a decrease of at least 0.3% in HbA1c at Week 12 (responders)

Safety Endpoints:

- Adverse events, laboratory, vital sign and electrocardiograms (ECG) parameters

Exploratory Endpoints:

- Plasma (non-genomic) biomarkers
- Diabetes treatment satisfaction questionnaire (s)
- Change from baseline in number of bolus injections of insulin
- An analysis of responders HbA1c < 7% without any severe hypoglycemic events, weight gain, ketoacidosis

Endpoints (Part 1, Interim analysis):

An interim analysis plan that will describe the variables of analysis. Endpoints will include, but not be limited to the following:

Primary Endpoints:

- Change from baseline in bolus insulin (number of units) OR
Change from baseline for time in target glycemic range (70-180 mg/dL)

Secondary Endpoints:

- Change from baseline for time in hyperglycemic range (Level 1 > 180 mg/dL; Level 2 (>250mg/dL) and hypoglycemic range (Level 1 < 70mg/dL; Level 2 < 54 mg/dL)
- Composite endpoint encompassing change from baseline HbA1c and risk of hypoglycemia as described in the SAP
- Change from baseline in average daily glucose

Safety Endpoints:

- Adverse events, laboratory, vital sign and electrocardiograms (ECG) parameters

Exploratory Endpoints:

- Change from baseline in basal or total daily insulin dose (number of units)
- Percent change from baseline in insulin (basal, bolus or total daily) dose
- Change from baseline glycemic markers (fructosamine and 1,5 anhydroglucitol)
- Body weight
- Glycemic variability (mean SD and CoV)

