10.2. Sample Size Determination

Assuming a standard deviation (SD) of 1%, 34 patients per group will provide 80% power to detect a difference between a group treated with TTP399 and the group treated with placebo of 0.7% in HbA1c using alpha = 0.049.

Randomization of 68 patients (34 patients randomized to each arm) will provide adequate power for this study to meet its objectives related to HbA1c changes.

Assuming 30% or fewer placebo-treated patients show improvement in HbA1c of 0.3% or better and assuming 60% or more patients treated with TTP399 will achieve improvement in HbA1c of 0.3% or better by Week 12, 49 patients per group will provide 80% power to

detect a difference between TTP399 and placebo. Randomization of N=120 patients into the study to be included in the Part 2 analyses provides adequate power to achieve study objectives related to responder analysis.

It is noted that the randomization stratification for part 2 will be reflected in the randomization identification with a stratum digit.

It is noted that in this adaptive study, modification is permitted.

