1.11 Modifications from the Statistical Section of the Protocol

This SAP is consistent with the protocol with the following exceptions:

- The primary analysis is characterized more completely with change based on blinded evaluations and communications with key opinion leaders. Modifications of the statistical analysis that represent departures from the protocol are permitted in an adaptive study, and such changes are explicitly allowed in the protocol.
- A conditional sequence of hypothesis tests has been modified to reflect blinded evaluations and communications with key opinion leaders.

Any other modifications will be documented in amendments to the SAP or the clinical study report.

2 Statistical Hypotheses

The primary objective is to show superiority (using a 2-sided test) of TTP399 to placebo at 12 weeks in patients treated with insulin on a dichotomous variable to delineate patients treated with insulin plus placebo from patients treated with modified insulin with TTP399 added followed by a non-inferiority evaluation of change in HbA1c followed by a superiority evaluation of change in HbA1c .

It is noted that the insulin optimization is applied to all subjects who are not already optimized in the opinion of the investigator. After the start of double-blind study medication, intensive medical monitoring results in modifications of insulin for all patients. Under the alternative hypothesis of treatment benefit, the modification of insulin for subjects on active treatment may be altered as a result of the co-administration of TTP399. Modification of insulin for subjects on placebo is considered standard of care. It is concluded, therefore, that the placebo added to insulin standard of care is the control group for treatment with TTP399 added to a modified regimen of insulin.

The statistical evaluation including non-inferiority evaluation and hypotheses to be tested in Part 2 are as follows:

First Compound Statistical Evaluation (full alpha):

The first evaluation is non-inferiority of treatment with TTP399 800 mg daily plus a modified regimen of insulin and treatment with optimized insulin as determined by the insulin-optimization period of the study, if needed, per protocol:

- Evaluation 1:**

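### The 0.3% HbA1c responder has three different timings in the protocol, and its scoring rule (before Week 12) contradicts the Week 12 endpoint without the SAP revoking it

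*Protocol*

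**What the plan says.** Three places in the protocol time the same responder differently.

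- **Endpoint list (Protocol 2.3, and the synopsis):** "Achievement of a decrease of at least 0.3% in HbA1c at Week 12 (responders". The amendment log for Amendment 5 records that the endpoint was clarified to this wording.
- **Sample size (Protocol 10.2):** the planning rates refer to improvement in "HbA1c of 0.3% or better by Week 12". SAP 1.9 repeats this text.
- **Scoring rule (Protocol 10.6.3):** "Patients obtaining achievement of the response criterion prior to Week 12 will be considered responders; all others will be considered non-responders". The section adds that no imputation is needed.

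Protocol section 10 lets the SAP supersede it for analyses. The SAP covers Part 2 only. SAP 6.1.2 repeats the endpoint with Week 12 timing, Evaluation 3 in SAP section 2 tests responders at Week 12, and SAP 7.5 imputes non-response for dichotomous variables. SAP 7.6.2 says secondary analyses also use observed cases and last observation carried forward. SAP 1.11 opens with "This SAP is consistent with the protocol with the following exceptions". It then names two exceptions, a fuller description of the primary analysis and a changed test sequence. Neither clearly covers the scoring of this secondary responder.

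**The concern.** A responder endpoint is only as clear as its scoring rule, and the one explicit scoring sentence in the protocol looks at the wrong visits. HbA1c responds slowly, so an earlier value may carry only part of a 12-week effect. A rule that uses earlier values can credit a transient fall and miss a response that arrives at the endpoint visit. Two programmers who both follow the documents could report different responder proportions, and a patient who leaves after an early response could be scored either way. For Part 1 the supplied SAP gives no answer, because it is confined to Part 2.

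**Working it through.** **1. How each wording scores a patient.** *By* is read here as any visit up to and including Week 12.

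| Earlier visit | Week 12 | At Week 12 | By Week 12 | Prior to Week 12 (literal) |
|---|---|---|---|---|
| met | met | responder | responder | responder |
| met | not met | non-responder | responder | responder |
| not met | met | responder | responder | non-responder |
| not met | not met | non-responder | non-responder | non-responder |
| met | missing | non-responder (SAP 7.5), or possibly responder (LOCF, SAP 7.6.2) | responder | responder |

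The wordings disagree in the second, third and fifth rows. Reading *prior to* as *by* repairs only the third.

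**2. Which earlier visits exist.** In Part 2, the HbA1c row of Appendix 2 shows Screening, Week 0, Week 6 and Week 12/ET. On that schedule the literal rule rests on Week 6, or on an early-termination value, and never on Week 12. Table 1 for Part 2 instead counts four double-blind HbA1c samples, so there may be one more earlier value. In Part 1, Appendix 2 gives Weeks 2, 4, 6 and 8.

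**3. The plan's own figure.** Inputs from Protocol 10.2 and 10.10:
- "Assuming 30% or fewer placebo-treated patients show improvement in HbA1c of 0.3% or better"
- "assuming 60% or more patients treated with TTP399 will achieve improvement in" the same criterion
- "49 patients per group will provide 80% power"
- "reserving 0.049 for the final analysis", two-sided

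With mean rate 0.45 and difference 0.30:

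n₀ = [1.969·√(2·0.45·0.55) + 0.842·√(0.3·0.7 + 0.6·0.4)]² / 0.30² ≈ 42.2, rounded up to 43.

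With continuity correction: n = (n₀/4)·[1 + √(1 + 4/(n₀·0.30))]² ≈ 48.7, rounded up to 49.

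The stated 49 is reproduced. Exact Fisher power at 49 per group is 81.5%. At the 45 per arm planned for Part 2 (SAP Table 1) it is 75.3%. Correcting the scoring rule leaves the rates and the formula alone, so 49 stands.

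**4. Illustration of the effect of timing.** The documents give neither the Week 6 effect nor the correlation between visits, so both are assumptions. The model is bivariate normal with one earlier visit (Week 6), correlation 0.7, and placebo at 30% at both visits. The Week 6 shift between arms is a share of the Week 12 shift, from one half to all of it. On the normal scale, 30% is −0.524 and 60% is 0.253, so the full shift is 0.778.

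TTP399 rate at Week 6: Φ(−0.524 + 0.5·0.778) = 44.6% at half effect, and 60% at full effect.

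Response at both visits: placebo 19.1%; TTP399 38.3% (half) or 47.8% (full).

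Response at either visit = Week 6 rate + Week 12 rate − both:
- placebo: 30 + 30 − 19.1 = 40.9%
- TTP399, half: 44.6 + 60 − 38.3 = 66.3%
- TTP399, full: 60 + 60 − 47.8 = 72.2%

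Week 12 responses lost under the literal rule = Week 12 rate − both:
- placebo: 30 − 19.1 = 10.9%
- TTP399: 60 − 38.3 = 21.7% (half), or 60 − 47.8 = 12.2% (full)

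Exact Fisher power, 45 per arm, alpha 0.049:

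| Share of effect at Week 6 | At Week 12 | Either visit | Literal (Week 6) |
|---|---|---|---|
| half | 75.3% | 58.6% | 22.3% |
| three quarters | 75.3% | 68.8% | 48.1% |
| all | 75.3% | 79.6% | 75.3% |

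**The case against.** The strongest reply is that the operative document already settles the timing. The SAP takes precedence, says Week 12 in 6.1.2 and in Evaluation 3, imputes non-response, and never repeats the rule. A Part 2 analysis run from the SAP should not be scored on Week 6 alone. This stands and takes most of the practical weight out of the point. It does not close it. SAP 6.1.2 repeats an endpoint label that already sat beside the conflicting rule in the protocol, no SAP sentence sets earlier visits aside, and the LOCF text in 7.6.2 sits unreconciled with 7.5.

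It is also fair that *prior to* may be a slip for *by*, given the wording of Protocol 10.2. That would restore first responses at Week 12 but would still credit lost ones.

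Three stronger readings might be inferred, and the documents do not support them:

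- **That trial success would be scored on earlier visits.** The 0.3% responder is outside Evaluations 1 to 7. The responder in the success rule is a different composite (SAP 6.1.1), which Evaluation 3 already places at Week 12.
- **That the rule must cost power or raise the placebo rate.** With the full effect at Week 6, the literal rule costs no power and the either-visit reading gains some. The placebo rate rises, from 30% to 41%, only under the either-visit reading. Under the literal rule it stays at 30% in this model.
- **That the planning rates of 30% and 60% are undermined.** The planning text says by Week 12, which is compatible with counting earlier responses.

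**Conclusion.** The inconsistency is real: one responder measure, three timings, and a scoring rule that contradicts the endpoint whether read literally or as a slip. It should be corrected, but its reach is limited. It touches a secondary endpoint outside the SAP's test sequence, and for Part 2 the superseding SAP already points to Week 12. What remains open is the unrevoked protocol sentence, its absence from SAP 1.11, the LOCF text for secondary endpoints, and Part 1, which this SAP does not cover.

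That patients can be classified differently follows from the wording alone. The size does not. The range of 59% to 80% (either visit) and 22% to 75% (literal) against 75% at Week 12, and the loss of a Week 12 response in about 11% of placebo and 12% to 22% of TTP399 patients under the literal rule, rest on the assumed correlation of 0.7, the assumed share of effect at Week 6, and a single earlier visit. They are illustrations, not forecasts.

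**What to change.** Before unblinding:

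1. In Protocol 10.6.3, replace the sentence with: *Patients meeting the criterion at Week 12 are responders; all others, including those with no Week 12 value, are non-responders.*
2. In Protocol 10.2, change *by* to *at* Week 12, and carry this into the copy in SAP 1.9.
3. List the change in SAP 1.11.
4. State in SAP 6.1.2 and 7.6.2 that earlier visits do not count for this endpoint. This also makes clear that a carried-forward value cannot make a responder.
5. Optionally, name Week 12 in the HbA1c component of the SAP 6.1.1 responder. This only confirms what Evaluation 3 already says.

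The cost is a sentence and a word in the protocol and a few lines in the SAP, with no new data and no change to the sample size. The downside is that patients who leave early after an earlier response become non-responders.
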